## 6.4 Safety measures

### 6.4.1 Types of safety events

The below definitions are based on ISO 14155.

#### 6.4.1.1 Adverse Event (AE)

Any untoward medical or dental occurrence, unintended disease or injury, or untoward clinical signs (including abnormal laboratory findings) in subjects, users or other persons, whether or not related to the Investigational Product or the procedures involved.

For users or other persons, this definition is restricted to events related to the Investigational Product.

**DENTSPLY Implants clarification:** Not only the Investigational Product, but also other medical devices used in the study, for example abutments and prosthetic parts should be included in the AE reporting.

A 'subject' is a patient who is treated within the frame of a clinical study.

A 'user' is a person handling the medical device, for example the dentist, nurse or assistant.

'Other persons' are someone else present in the room during the treatment, for example a friend of the patient.

#### 6.4.1.2 Adverse Device Effect (ADE)

AE related to the use of an Investigational Product.

This includes AEs resulting from insufficient or inadequate instructions for use, deployment, implantation, installation, or operation, or any malfunction of the device. This includes any events resulting from use error or from intentional misuse of the device.

**DENTSPLY Implants clarification:** Not only the Investigational Product, but also other medical devices used in a study, for example abutments and prosthetic parts should be included in the ADE reporting.

#### 6.4.1.3 Serious Adverse Event (SAE)

An SAE is an AE that:

- Led to death,
- Led to a serious deterioration in the health of a subject, that either resulted in
  - a life-threatening illness or injury, or
  - a permanent impairment of a body structure or a body function, or
  - in-patient or prolonged hospitalization (Hospital admissions and/or surgical operations that were planned before or during the study for a pre-existing condition, without serious deterioration in health, is NOT considered an SAE), or
  - medical or surgical intervention to prevent life-threatening illness or injury or permanent impairment to a body structure or a body function.

- Led to fetal distress, fetal death or a congenital abnormality or birth defect.

#### **6.4.1.4 Serious Adverse Device Effect (SADE)**

An SADE is an ADE that has resulted in any of the consequences characteristic of an SAE.

#### **6.4.1.5 Device Deficiency**

Inadequacy of a medical device with respect to its identity, quality, durability, reliability, safety or performance. This includes malfunctions, use errors, and inadequate labeling.

**NB!** Pay special attention to device deficiencies that might have led to an SADE if:

- a) suitable action had not been taken or
- b) intervention had not been made or
- c) circumstances had been less fortunate.

**DENTSPLY Implants clarification:** A device deficiency is an event associated with the product itself, not with the subject. The loss of an implant is not defined as a device deficiency; it is defined as an ADE.

#### **6.4.2 AE and ADE recording and reporting**

In clinical studies, an AE can include a health/oral problem occurring at any time, including run-in or follow-up periods, even if the subject has not been exposed to the medical device.

Subjects will be observed and asked about 'any health or oral health problems since last visit' during the study.

All health/oral problems, reported by the subject, found in medical records or found at the clinic visits, must be recorded in the eCRF as an AE. Information that will be collected includes:

- Event description
- Start date
- Stop date or event continuing
- Serious yes/no
- Device/procedure related yes/no
- Action taken due to the event
- Clinical outcome of event

If an AE is assessed to be device/procedure related it is defined as an ADE. For ADEs the Investigator must:

- record ADE details in the eCRF as soon as he/she becomes aware of it, an e-mail will automatically be sent to DENTSPLY Implants

If an AE/ADE results in a subject's discontinuation in the study, this should be recorded on the Termination page in the eCRF. Not only the Investigational Product, but also other medical devices used in a study, for example abutments and prosthetic parts should be included in the ADE reporting.

Examples of AEs are e.g. cold, headache and abutment loss at non-study positions.

Examples of ADEs are e.g. implant loss, implant fracture, abutment loss, abutment fracture, abutment screw fracture, abutment loose, bridge screw loose/fractured at study positions.

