OHIP-14 includes seven domains and is therefore able to cover a wide range of possible oral health problems that may have an impact on quality of life. The domains are: functional limitation, pain, psychological discomfort, physical disability, psychological disability, social disability and handicap. OHIP attempts to measure both the frequency and severity of oral problems on functional and psychosocial well-being. An example of an OHIP statement is "Have you had to interrupt meals because of problems with your teeth, mouth or dentures". Responses are based on a Likert scale (i.e., 0 = never, 1 = hardly ever, 2 = occasionally, 3 = fairly often, 4 = very often).

- ***Implant success***

Implant success will be evaluated as defined by the ICOI Pisa Consensus Conference 2008 [35]. An implant will be considered successful if all of the following criteria are fulfilled:

- Implant still in place
- No mobility
- No pain or tenderness upon function
- <2 mm marginal bone loss from initial surgery to 5-year follow-up visit
- No history of exudates

- ***Prosthetic survival***

A prosthetic restoration will be considered a *survivor* if the original restoration is still in place at the follow-up visit, regardless of its condition.

- ***Prosthetic success***

A prosthetic restoration will be considered as successful if it has remained unchanged and there has been no need of technical repair during the observation period.

The occurrence of any technical repair of the prosthesis or any biological complications related to the prosthesis will be registered and reported as ADEs (section 6.4.1.2).

- ***Number of avoided augmentations***

The proportion of augmentations avoided by using six 6.6 mm implants instead of six 8.0 mm implants will be virtually evaluated by using the SIMPLANT file generated from the CBCT at Visit 2. First, six regions of interest will be defined in SIMPLANT by indicating the mesial and distal borders of the canine, premolar and molar regions on both left and right side. An evaluator, independent from the investigational group and DENTSPLY Implants, will then make a surgical planning with six 6.6 mm implants placed at the pre-defined canine, premolar and molar regions and count the number of sites that would need augmentation. The evaluator will then repeat this

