### 8 Investigational Products

Product Name	ANKYLOS® C/X Implant A 6.6
Diameter	3.5 mm
Lengths	6.6 mm
Characteristics	Dental endosseous implant

Packaging	Sterile, double package
Other products	
Cover screws	ANKYLOS® C/X Cover Screw
Abutments	ANKYLOS® Balance Base Abutment C/ narrow – available in four heights, i.e. 0.75, 1.5, 3.0 and 4.5 mm. Both the straight (A0) and the 15° angled (A15) abutments are allowed in the study. NB! The 30° angled versions (A30) are not allowed in the study.
Suprastructure	Occlusally screw-retained ATLANTIS™ ISUS bridges (titanium)
Veneering	Subjects will, in consultation with the Investigator, be able to choose one out of four alternatives: 
 
• Resin
 
• Composite
 
• Composite and Ceramic
 
• Ceramic
 

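### Section 6.4.2 merges device and procedure relatedness in one yes/no item, so surgery-only events count as ADEs although the ADE definition does not include them

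*Combined protocol and SAP*

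**What the plan says.** Section 6.4.1.2 gives the base definition of an ADE: "AE related to the use of an Investigational Product". Section 8 names "ANKYLOS® C/X Implant A 6.6" as that product and lists cover screws, abutments, suprastructure and veneering as other products. A sponsor clarification in 6.4.1.2, repeated in 6.4.2, widens the scope to other study devices: "for example abutments and prosthetic parts should be included in the ADE reporting". Neither the definition nor the clarification adds the procedure as a cause.

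Section 6.4.2 lists the information collected for each event. Causality is one item, "Device/procedure related yes/no", and the consequence is "If an AE is assessed to be device/procedure related it is defined as an ADE". Under Prosthetic success, section 6.3.2.2 adds: "The occurrence of any technical repair of the prosthesis or any biological complications related to the prosthesis will be registered and reported as ADEs".

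On device deficiencies, section 6.4.1.5 covers inadequate durability, reliability and performance, includes malfunctions, and clarifies: "A device deficiency is an event associated with the product itself, not with the subject". It assigns only one event expressly, implant loss, which is an ADE and not a deficiency. Section 6.4.2 says "Examples of ADEs are e.g. implant loss, implant fracture, abutment loss, abutment fracture, abutment screw fracture" and goes on to loosening and bridge-screw events. The sole deficiency example, in 6.4.4, is damaged packaging.

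Section 2.3 names ADEs, SADEs and device deficiencies as safety outcomes. Section 10.3 plans descriptive statistics only for safety and specifies no split by component or cause.

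**The concern.** The definition and the recording rule do not match. A purely surgical complication, with no role for implant, abutment or bridge, falls outside 6.4.1.2 but becomes an ADE under 6.4.2. Through 6.4.1.4 it becomes a SADE if it is serious.

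The trial has one arm, so no control group shows the procedural background, and the safety results are counts and percentages. The classification rule therefore largely decides what the ADE table says. A reader would take an ADE frequency as a statement about the device, whereas the number mixes implant, abutment, bridge and surgery.

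The fracture question is a smaller matter of the same kind. Investigators must say whether an event led or could have led to a SADE only on the deficiency path in 6.4.4. If sites differ on whether a fractured component goes down that path, the deficiency count is not comparable across the three to four sites, and that question may go unanswered for some fractures.

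**Working it through.** The plan states no figure on this point, so the check sets the sections side by side.

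**Device versus procedure**

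1. The AE definition in 6.4.1.1 names the Investigational Product and the procedures as two separate possible causes, so the plan recognises the distinction.
2. The ADE definition in 6.4.1.2 uses only the first cause. It also takes in events from inadequate instructions, malfunction, use error and misuse, so some surgical events qualify properly. The clarification adds other devices.
3. Section 6.4.2 joins the two causes with a slash in one yes/no item and makes every yes an ADE.
4. The events in (3) that are not in (2) are those judged related to the procedure and to no device. These are the misclassified events.
5. The other listed items are description, dates, seriousness, action taken and outcome. None records which cause the investigator had in mind, and nothing requires the description to state it.
6. Section 10.3 plans no breakdown that would separate them.

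**What can be separated afterwards**

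Section 6.3.1.1 counts every lost or removed implant as a failure of the primary outcome, whatever the reason. Section 10.2 puts all subject data in listings, and each event has a description. Implant loss or fracture can therefore be told apart from a bridge repair. The causality judgement cannot, unless the free text happens to give it.

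**Fractures**

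1. A broken component can fit 6.4.1.5 through durability or malfunction, although that section never names fractures.
2. It can also be an ADE, because 6.4.1.2 includes events from malfunction and 6.4.2 lists fractures as examples.
3. The two categories are not declared mutually exclusive, except for implant loss.
4. No sentence says whether a fracture is entered as an ADE, a deficiency or both.

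**Size**

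The documents give no rate for procedure-related events or for any ADE other than implant loss, so no magnitude follows from them. The following shows only how little a pooled total reveals about the implant. Inputs are 56 subjects with 6 implants each (sections 4.1 and 10.4) and the plan's assumed survival of 95% to 93% (section 10.4), ignoring drop-out and counting one ADE per lost implant. The rate of all other ADEs is my assumption, 0.25 to 2 per subject.

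- Implants: 56 × 6 = 336.
- Losses: 336 × 0.05 = 16.8 to 336 × 0.07 = 23.5.
- Other ADEs: 56 × 0.25 = 14 to 56 × 2 = 112.
- Share of implant loss at 95% survival: 16.8/(16.8 + 14) = 55% down to 16.8/(16.8 + 112) = 13%.
- Share at 93% survival: 23.5/(23.5 + 14) = 63% down to 23.5/(23.5 + 112) = 17%.

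The share depends almost entirely on the assumed rate. This is not an estimate of the procedure-only fraction, for which the documents offer nothing.

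**The case against.** The case on the other side has real weight.

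- Pooling of devices is deliberate. The sponsor states it in 6.4.1.2 and repeats it in 6.4.2, so including abutments and bridges is a broad reporting rule and not a slip. This stands. The inconsistency is confined to the procedure, which no definition adds.
- The implant's performance is measured elsewhere, through survival, stability, marginal bone level, radiolucency and the success criteria. Prosthetic survival and success have their own intervals. This also stands. A reader might infer that the trial cannot show the implant's safety at all; the documents do not support that.
- The eCRF itself is not in the documents, and the list in 6.4.2 is introduced as what the information includes. The form may record the component. That is possible, but the plan does not say so, and the combined causality item is explicit.
- SAEs and SADEs share the same reporting steps and deadline in 6.4.3, so calling a serious surgical event a SADE delays nothing. Correct: the effect is on the reported tables, not on expedited reporting.
- A reader might infer that 6.4.1.5 classes fractures as deficiencies, or that a site following the examples will never record one as such. Neither follows. The section does not mention fractures, both sets of examples are illustrative, and 6.4.4 requires an entry for every deficiency. What remains is a missing instruction on dual recording.

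**Conclusion.** The point holds in a limited form. Sections 6.4.1.2 and 6.4.2 disagree on whether a procedure-only event is an ADE. Under 6.4.2 such events enter a named safety outcome as device effects, and the listed items cannot take them out again except through free text. With no planned breakdown, the pooled ADE total does not describe device-related or implant-related safety. The primary analysis is unaffected.

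The size is unknown. A reader might infer that ADE frequency will mostly reflect surgery and veneers, but the plan has no rates to support that. The conclusion rests on sites following 6.4.2 as written and on the eCRF holding no causality items beyond those listed.

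The secondary point is an unsettled boundary: fractures can meet both definitions, no rule assigns them, and site practice may differ.

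**What to change.** - In 6.4.2, replace the combined item with three yes/no items: related to the study implant, to another study device (abutment, screw, bridge), and to the procedure. More than one may be yes.
- Define an ADE, and hence a SADE, by the two device items only. Events from use error or inadequate instructions stay in through those items, as 6.4.1.2 already intends.
- In 10.3, tabulate ADEs and SADEs by component and show procedure-related events separately.
- Reconcile 6.4.1.5, 6.4.2 and 6.4.4 by stating that a component fracture or malfunction meeting the deficiency definition is recorded both as an ADE and as a device deficiency. Implant loss remains an ADE only. A compulsory deficiency entry for every loosening is not proposed, since 6.4.1.5 does not treat loosening as product inadequacy in itself.

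The cost is an eCRF item split, revised site instructions and an occasional dual entry. No visit, assessment or treatment changes.

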#### **6.4.3 SAE and SADE recording and reporting**

SAEs and SADEs have to be reported to DENTSPLY Implants as soon as the Investigator becomes aware of it.

For SAEs/SADEs the Investigator must:

- Record SAE/SADE details in the eCRF immediately, but no later than the end of the next business day (counting from when the Investigator becomes aware of the SAE/SADE), an e-mail will automatically be sent to DENTSPLY Implants
- Follow up the initial SAE/SADE information as soon as new information is available.
- Inform the responsible IEC/IRB of SAEs/SADEs, as per local requirements. This may involve both those SAEs/SADEs occurring at the study site as well as at other participating study sites (this information will be provided to the Investigator by DENTSPLY Implants, if required).
- Inform the responsible Regulatory Authority of SAEs/SADEs, as per local requirements. This may involve both those SAEs/SADEs occurring at the study site as well as at other participating study sites (this information will be provided to the Investigator by DENTSPLY Implants, if required).
- Provide DENTSPLY Implants with all SAE/SADE related documentation and correspondence to the IEC/IRB and Regulatory Authority

In addition, further attempts to speak directly with DENTSPLY Implants should be made by dialing the following [contact] and ask for responsible STL.

A copy of the SAE/SADE Report and associated documents must be filed in the ISF by the Investigator.

Examples of SAEs are e.g. broken leg requiring hospital admission and heart attack.

#### **6.4.4 Device Deficiency Reporting**

The Investigator is responsible for recording the following in the eCRF for all device deficiencies:

- Device deficiency details (e. g. date and description of occurrence)
- Whether the device deficiency led or could have led to a SADE

Pay special attention to device deficiencies that might have led to a SADE if:

- a) suitable action had not been taken or
- b) intervention had not been made or
- c) circumstances had been less fortunate

For device deficiencies that fulfil the SADE definition the Investigator must complete and provide DENTSPLY Implants with detailed information and perform the steps described for SAE/SADE reporting.

An example of a device deficiency is when the packaging around the implant is damaged.

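### Section 6.4.4 has sites flag device deficiencies that could have led to a SADE, but its expedited-reporting trigger, read literally, leaves those near misses out

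*Combined protocol and SAP*

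**What the plan says.** Section 6.4.4 puts three duties on the investigator.

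- Every device deficiency goes into the eCRF with its details and a flag: "Whether the device deficiency led or could have led to a SADE".
- Near misses are singled out. The section says "Pay special attention to device deficiencies that might have led to a SADE if" and then lists three conditions: had nobody acted, had nobody intervened, or had luck been worse. Section 6.4.1.5 carries the same list.
- The expedited duty comes last: "For device deficiencies that fulfil the SADE definition the Investigator must complete and provide DENTSPLY Implants with detailed information", together with the steps that 6.4.3 sets for SAEs and SADEs.

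The terms are defined earlier. Section 6.4.1.2 defines an ADE as an "AE related to the use of an Investigational Product". Section 6.4.1.4 states: "An SADE is an ADE that has resulted in any of the consequences characteristic of an SAE". The sponsor's clarification in 6.4.1.5 states: "A device deficiency is an event associated with the product itself, not with the subject".

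**The concern.** The flag and the trigger use different tests. The flag asks about potential for a SADE; the trigger asks whether a SADE exists. The category that 6.4.1.5 and 6.4.4 both stress, a defect that did no serious harm but might have, is therefore identified by the site and then given no stated route to prompt reporting.

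At stake is the speed with which the sponsor learns of a product problem that could recur at another site. Section 7.7 allows the sponsor to end the study on safety grounds, and a near miss is one of the signals on which such a judgement would rest. This is a matter of safety reporting only.

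**Working it through.** The plan gives no figure to reproduce, so the check traces the definitions through the reporting rules.

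**Step 1: what meets the trigger.** A SADE must be an ADE (6.4.1.4), and an ADE must be an AE (6.4.1.2). The ADE must also have had one of the consequences listed for an SAE in 6.4.1.3. The item on that list closest to a near miss is "medical or surgical intervention to prevent life-threatening illness or injury or permanent impairment to a body structure or a body function". Some averted harm is therefore already inside the SADE definition. That item is, however, one of the results of a serious deterioration in a subject's health, so it still needs an event in a person. A defect noticed before it affects anyone does not qualify, nor does one that passed without effect by good fortune.

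**Step 2: apply this to deficiencies.** By 6.4.1.5 a deficiency is a product event. There are three cases:

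- It led to a SADE. The SADE is already reportable under 6.4.3, with or without the trigger in 6.4.4.
- It could have led to a SADE but did not. No SADE exists, so the trigger is not met.
- It had no such potential. The trigger is not met, and the plan does not single out these cases.

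Read literally, the trigger adds little in the first case and misses the second.

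**Step 3: compare the stated rules.**

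| Event | Time limit | Automatic e-mail to sponsor | Further steps stated |
|---|---|---|---|
| SAE or SADE (6.4.3) | At once, at latest by the end of the next business day | Yes | Direct contact with sponsor; ethics committee and authority per local requirements |
| Non-serious ADE (6.4.2) | As soon as the investigator is aware | Yes | None beyond the eCRF details |
| Deficiency meeting the SADE definition (6.4.4) | As 6.4.3 | As 6.4.3 | As 6.4.3 |
| Deficiency that could have led to a SADE (6.4.4) | None stated | None stated | None stated |

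A loose bridge screw, listed as an ADE in 6.4.2, thus has a faster stated route to the sponsor than a product defect with potential for serious harm.

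**Step 4: look for the missing rule elsewhere.**

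- Section 3.1 names SAEs and SADEs for notification to committees and authorities. It also promises safety updates to principal investigators, as locally required.
- Section 3.2 binds both parties to their ISO 14155 responsibilities in general terms.
- Section 7.2 provides regular monitor contact, source verification and accountability checks.
- Section 8.3 requires destroyed product to be accounted for.
- Section 9.1 saves eCRF entries to a central database as soon as they are made.

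None of these sets a deadline for entering a deficiency or attaches an alert to one.

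**Exposure.** 56 subjects × 6 implants = 336 planned study implants, at three to four sites. This counts opportunities for a deficiency; it does not measure risk.

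**The case against.** The best defence is that the trigger sentence directly follows the near-miss list. Since a product event cannot itself be a SADE, the literal reading leaves the sentence almost nothing to do, and the reading that gives it effect is that it covers the near misses just described. As an account of intent this is persuasive, and it is why a slip of wording is the likely explanation. It does not make the text safe to follow, because a site that applies the definitions as printed would not expedite a near miss.

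Several stronger readings are tempting, and the documents do not support them.

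- A reader might infer that a defect could stay unseen in one site's eCRF. Section 9.1 rules that out once the entry is made. What is missing is a date by which to make it and a prompt to look at it.
- A reader might infer that there is no escalation of any kind. Monitoring, accountability checks, safety updates and the ISO 14155 clause are all routes, although none carries a deadline. What ISO 14155 requires here cannot be checked from these documents. Nor can the eCRF set-up, so an alert may exist that the plan does not mention.
- A reader might infer that fractures escape the system, because 6.4.2 says "Examples of ADEs are e.g. implant loss, implant fracture, abutment loss, abutment fracture, abutment screw fracture" while 6.4.1.5 counts poor durability as a deficiency. Section 6.4.1.2 places events from device malfunction among ADEs, so the listing is consistent, and an ADE entry alerts the sponsor. Nothing prevents a site from also entering a fracture as a deficiency. Compulsory double entry is not needed, and an undercount of the Device Deficiency outcome in 2.3 would be conjecture about site behaviour.

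It is also fair to say that damaged packaging is offered in 6.4.4 as an example of a deficiency, not of a near-miss SADE.

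**Conclusion.** The point stands as a defect in one stated rule. Taken at its word, the trigger in 6.4.4 excludes deficiencies that could have led to a SADE but did not. Those cases are recorded, flagged and centrally visible after entry, yet have no stated time limit, alert or onward reporting step.

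The conclusion rests on reading 6.4.1.4 and 6.4.1.5 literally and on the plan's text alone; a study manual or eCRF specification might fill the gap in practice. With no deficiency rate in the documents, the number of affected reports cannot be estimated. There is no effect on sample size, power or the primary analysis. The change should be made because it is cheap and bears on subject safety.

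**What to change.** In 6.4.4, replace the condition that a deficiency meets the SADE definition with the test the section already uses for its flag: any deficiency that led, or could have led, to a SADE. Keep the link to 6.4.3, so that its next-business-day limit, automatic e-mail and reporting steps, including those that depend on local requirements, apply to these deficiencies. Nothing else in 6.4 needs to change.

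The cost is a change of wording in one sentence, handled under 7.1, an e-mail trigger on the deficiency form in the eCRF, and a few more expedited reports. Some of those reports will concern defects that prove harmless.
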